**Outline of organizational structure of the multicenter protocol**

All recruitment, enrollment, and data collection will take place at Clínica de Familia La Romana, in the Dominican Republic. [name], a postdoctoral fellow at Columbia University and co-investigator on this study, will be on-site throughout the course of the study and will be responsible for all administrative duties, subject/data/site monitoring, and will also facilitate communications and lead all data analysis. Clínica de Familia is in the process of obtaining and FWA number. Once it is obtained, it will be provided to the IRB prior to any study activities beginning.

[name], a postdoctoral fellow at Columbia University and co-investigator on this study, will be responsible for reviewing and reporting all adverse events. She will be responsible for training any local study team members to identify and report any adverse events.

[name] will be in charge of maintaining records of all IRB/ethics committee review and approval of all protocol and consent forms for all collaborating sites for the duration of the study. She will apply for a renewal at least 60 days prior to the end of the approval period at CUMC's IRB. CONABIOS, the ethical review board in the Dominican Republic, does not require renewals for approved protocols.

[name] will be responsible for all administrative duties, subject/data/site monitoring, facilitating communication, and data analysis. She is working on this study as part of an NIH funded career development award and will be monitored closely by her mentoring team who are all indicated as co-investigators on this study.

**Provide a description of the responsibilities of the coordinating center / lead institution with regard to communication and training of research personnel across sites:**

[name], a postdoctoral fellow at Columbia University, will be the point person for communication with Columbia University. She has already received training in the protection of human research subjects.

[name] will also be in charge of training any local staff to ensure accurate and consistent instrument training and data management across sites. She will also oversee all study procedures at Clínica de Familia La Romana. All data will be entered into encrypted tablets into Columbia University's REDCap Survey Management Software. No special equipment is needed for data transfer.

[name] will meet individually with any local study team members daily at the beginning of the study to ensure that all procedures are being carried out correctly, that the study protocol is well understood, and that everything is completed in a confidential and ethically appropriate way.

**Provide a plan to ensure that collaborating sites do not begin any research-related activity until IRB approval has been granted for the conduct of research at that site:**

[name] will be responsible of overseeing all research activities at Clinica de Familia La Romana and will not begin data collection until all IRB approvals have been obtained.

**Provide a description of the transmission of data to the data coordinating center:**

All study data will be stored on an encrypted password protected Columbia University Computer and will be on Columbia University Servers. Data will be collected on an encrypted tablet into Columbia University's REDCap Survey Management Software. No data will be stored on the tablets. Any data that needs to go back and forth between CUMC and the DR will be saved in these servers as [name] will have access to them both in the Dominican Republic and on the CUMC campus. [name] will review all data for completeness as it is being collected and will be responsible for obtaining any missing data and correcting any errors that she finds. All participant information will be stored on Columbia University servers that [name] will be able to access both from the study site in the Dominican Republic and from the CUMC campus. If any data needs to be transmitted beyond the servers, it will be de-identified and shared through secure Columbia University email accounts.

### **Specify how and where the data will be analyzed and who is responsible for the analysis(es):**

Data will be analyzed using the methods that are detailed in the procedures section. [name] will be responsible for data analysis. She consistently travels back and forth between the Dominican Republic and the CUMC campus so data analysis will take place in both sites.

### **Study Purpose and Rationale**

The Caribbean has among the highest HIV prevalence in the world. Regionally, the majority of HIV/AIDS cases are located on the island of Hispaniola, comprised of the Dominican Republic (DR) and Haiti. Due to a large international response and widespread availability of antiretroviral therapy (ART), in recent years the incidence of HIV in the DR has declined and prevalence hovers around 1% in the general population. The effective and long-term management of this condition depends on infected individuals being able to acquire ART and apply the learned information and self-management skills that lead to optimal adherence.

HIV-related disparities exist in developing countries, such as the DR, where minority groups and/or those with low socioeconomic status experience higher disease burdens and worse health outcomes than those with higher socioeconomic status. These disparities may be exacerbated when individuals are unable to understand the health information, as low health literacy has been associated with worse health outcomes, less use of healthcare services, poorer knowledge of illness, and worse self-management. The effective management of HIV requires patients to acquire, comprehend, and use large amounts of complex information, including how to manage variations in health status, medications and their side effects, nutrition and exercise needs, and healthy coping. Health care providers can help patients understand pertinent health information by offering it in targeted, culturally-, language-, and literacy-appropriate ways.

One such strategy is to use infographics to assist communication through visual representations of information. Participatory design of infographics supports presentation of information in a culturally appropriate and visually appealing format which can improve information understanding, health behaviors, attention span, and ability to recall information. It is critical to develop and test methods to improve the way health information is delivered to patients in these clinical contexts so patients, including those with low health literacy, can acquire and comprehend the information needed to improve self-management behavior and treatment outcomes.

Preliminary studies (T32 NR013454) showed many persons living with HIV (PLWH) attending Clínica de Familia La Romana do not fully comprehend and use the health information they receive through current modalities. In response, culturally relevant, evidence-based infographics to improve information delivery during clinical visits were developed (T32 NR007969) with a participatory design methodology (manuscript under review). The next phase of this study is to rigorously assess if using these infographics is a feasible, acceptable, and efficacious method to enhance HIV-related clinician-patient communication and lead to improved patient outcomes. Additionally, a thorough exploration into the cultural factors of patient-provider communication in the Dominican Republic that can influence infographic use for clinician-patient communication in a clinical setting is warranted.

**The purpose of this study is, therefore, to complete the following research aims:**

**Aim 1.** Explore the usability of infographics (designed during preliminary studies) to facilitate HIV-related clinician-patient communication and to assess their feasibility using established guidelines.

**Aim 2.** Pilot test measures to assess treatment outcomes within this population and estimate measurement parameters for future efficacy testing (means and standard deviations).

**Aim 3.** Measure the effect of infographic use on PLWH's treatment outcomes at three-, six- and nine-month intervals following initial exposure to the intervention.

**Aim 4.** Generate an explanatory model of HIV infection among patients in this clinical context and explore how it may be used to guide HIV-related communication using infographics.

## **Study Design**

To complete the study aims, a mixed methods study that includes a single group pretest posttest study design will be used to pilot test the infographic intervention. In-depth interviews will be completed with a selection of participants to explore participant perceptions of HIV-related communication using infographics. Data will be collected from participants through baseline (at enrollment) and follow up assessments (at 3-, 6-, and 9-month follow up visits). Follow up interviews will be conducted with the providers involved in the intervention to ascertain their perspectives on the clinical utility of infographics. Participant's most recent CD4 count and viral loads will be collected from participants' medical records at each study visit.

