Participant eligibility will be verified in the medical records of patient's scheduled appointments at the beginning of each day. Eligible participants will then be recruited by the receptionist when they present to the Clinic for their regular clinic visit and referred to speak to an on-site researcher who will further introduce the study (see attached recruitment script) and then if a participant is interested, complete the informed consent process. After completing the informed consent process, participants will complete a baseline assessment using REDCap software with the help of a study team member prior to their visit (Table 1). Participants will then receive the intervention during the enrollment visit and at three and six-month visits and complete the follow up assessment at each of these time. Time intervals were selected as CD4 count and viral load may change as early as three months after ART initiation. Interventionists will time visits and no extra time will be allowed for study visits. Following their six-month study visit, participants will be asked to participate in in-depth interviews. At the nine-month study visit, participants will complete a follow up assessment to assess ability to recall information from infographics over time. At the end of the study, the interventionists will be interviewed to assess feasibility of infographic use in a clinical setting.

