## Measures

Outcome selection was guided by a conceptual model to theoretically guide communication studies. This model illustrates pathways through which clinician-patient communication may influence health outcomes in the short (proximal), medium (intermediate), and long-term. Primary outcomes of CD4 count and viral load will be collected from patient medical records at each study visit. Measures of information recall/comprehension, engagement with clinician, satisfaction with care, self-efficacy to manage HIV, adherence, health related quality of life, and health status (self-reported status and CD4 count and viral load) will all be included in the baseline and follow up assessments.

**Baseline assessments** will collect demographic information, evaluate health literacy level, and contain the instruments to assess outcome measures.

**Follow up assessments for PLWH** will include the outcome measures as well as open-ended questions exploring the usability of infographics, satisfaction with designs and recommendations for improvement. Open-ended questions regarding interventionists' communication strategies and intervention delivery will be included to assess providers' communication variability. Participants' responses to open-ended questions on the follow up assessments will be audio-recorded with participants' permission and then transcribed to enable more effective analysis.

**Follow up interview for health care providers.** Interventionists will complete a semi-structured interview containing questions on the following aspects of feasibility: acceptability, demand, implementation, practicality, adaptation, integration, expansion, and limited-efficacy testing and

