**Table 1. Research activity at each time point**

Time point	Activity
Enrollment	
 
• Health literacy assessment
 
• Baseline assessment
 
• Exposure to intervention
 

3 months	
 
• Exposure to intervention
 
• Follow-up assessment
 

6 months	
 
• Exposure to intervention
 
• Follow-up assessment
 

9 months	
 
• Follow up assessment
 

Study end	
 
• Follow-up interview for health care providers
 

Note: In-depth interviews will take place after participant's 6 month visits

questions elucidating feedback on infographic design and suggestions regarding their effective incorporation into clinical visits.

**In-depth interviews with PLWH.** To describe PLWH's perceptions of HIV-related communication in a clinical setting and how it may be influenced by infographic use, directed content analysis guided by McGuire's Classic Input-Output Framework for Constructing Persuasive Messages will be used. In-depth interviews will be conducted using a semi-structured interview guide in a private setting by a study team member and will be audio-recorded and transcribed.

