## Statistical analysis plan

Sample size estimation was based on the recommendation of having 35-40 participants to pilot test instruments, thereby estimating the associated treatment effects. To account for 20% attrition (2% over the average rate in health behavior change trials to account for difficulties in retention associated with this population), 50 participants were recruited. Adults ( $\geq 18$  years of age), living with HIV, with a detectable viral load ( $\geq 40$  copies/mL) on their most recent laboratory test, who were planning to receive care at the Clinic during the study period, were eligible to participate.

We first characterized the study sample using descriptive statistics. Means and standard deviation and frequency analysis were performed on baseline demographic characteristics. Next, descriptive statistics of all outcome measures were performed, stratified by time point (baseline, 3-, 6-, and 9-months). Means and standard deviations were then computed for outcomes that roughly follow normal distribution and median and interquartile range were computed for skewed variables. So as not to inflate type II error, statistical analyses were only conducted for a subset of outcome variables, selected based on our theoretical model. The variables analyzed were: HIV-related knowledge, self-efficacy to manage HIV, CD4 count, viral load, current health status, and engagement with clinicians. Descriptive statistics of the remaining outcome variables were calculated.

To determine appropriate tests of association, tests for normality were conducted on all variables. If they were skewed, we log transformed variables to determine if skewness improved. The variables that met normality assumptions were then analyzed using general linear regression and those that were heavily skewed were analyzed using Wilcoxon signed-rank tests.

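### CD4 count and viral load are taken as the latest chart value with no draw-date rule, so a result drawn before first exposure can stand as a follow-up primary outcome, mainly at 3 months

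*Protocol*

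**What the plan says.** Protocol, Study Design: "Participant's most recent CD4 count and viral loads will be collected from participants' medical records at each study visit". Protocol, Measures, gives these values their rank: "Primary outcomes of CD4 count and viral load will be collected from patient medical records at each study visit".

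Aim 3 in the Protocol's list of aims concerns "treatment outcomes at three-, six- and nine-month intervals following initial exposure to the intervention". First exposure is at enrolment: "Participants will then receive the intervention during the enrollment visit and at three and six-month visits" (Protocol, Intervention). The same section explains the visit spacing: "Time intervals were selected as CD4 count and viral load may change as early as three months after ART initiation".

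The SAP (Statistical analysis plan) fits a GEE regression to CD4 count and log-transformed viral load. Its covariates are nominal time (baseline, 3, 6, 9 months) and whether the patient was new to the clinic, meaning under 3 months' attendance.

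For eligibility, the SAP asks for a detectable viral load (at least 40 "copies/mL) on their most recent laboratory test". The Protocol (Intervention) says when this is checked: "Participant eligibility will be verified in the medical records of patient's scheduled appointments at the beginning of each day".

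Neither document gives a draw-date window, a maximum age for the baseline result, a rule that follow-up results post-date exposure, a bar on using one result at two visits, or a coding rule for undetectable values before the log is taken. Table 1 of the Protocol lists no blood draw, though routine clinic tests need not appear there.

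**The concern.** Followed exactly, the rule labels a value by the visit at which the chart was read, not by when blood was drawn. A patient with no new test between enrolment and month 3 contributes the same result as baseline and as the 3-month outcome. A patient whose baseline test was months old contributes a change that began before the study. Aim 3 is about change after first exposure, and neither value measures that.

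Viral load has a second, separate problem. Eligibility is judged on the latest chart result that morning, and baseline is the latest chart result at that visit. Read together, these make baseline the qualifying value. Patients selected on a high reading tend to read lower next time. CD4 count is not an eligibility criterion, so this does not apply to it.

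The design has one group, so no control arm removes either effect. The means and SDs that Aim 2 wants for later trials would carry the same timing error.

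**Working it through.** **The plan's own figure.** The sample size is 40 / (1 - 0.20) = 50, which reproduces the SAP. This point does not affect it.

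**Timing of results.** The documents give no test frequency, so the interval T is an assumption. Suppose tests fall regularly every T months, at random phase relative to enrolment, with results available at once. At the visit in month v, the age of the latest result is uniform on 0 to T, so:

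- share of values drawn before exposure = max(0, 1 - v/T)
- share of visits with a result new since the last visit = 3/T

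| Test interval T (months) | 3 | 4 | 6 | 12 |
|---|---|---|---|---|
| Pre-exposure, month 3 | 0% | 25% | 50% | 75% |
| Pre-exposure, month 6 | 0% | 0% | 0% | 50% |
| Pre-exposure, month 9 | 0% | 0% | 0% | 25% |
| Visits with a new result | 100% | 75% | 50% | 25% |

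If blood is instead drawn at 3-monthly visits and reported afterwards, every 3-month value is the enrolment-day draw.

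**Effect on the 3-month change.** The direction depends on what happened before enrolment.

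| Test interval T (months) | 3 | 4 | 6 | 12 |
|---|---|---|---|---|
| No prior trend, immediate effect: share of true change seen (3/T) | 100% | 75% | 50% | 25% |
| No prior trend, linear effect: share seen (1.5/T) | 50% | 37.5% | 25% | 12.5% |
| Steady prior trend: share of 3-month change seen | 100% | 100% | 100% | 100% |
| Of that, share accrued before enrolment (1 - 1.5/T) | 50% | 62.5% | 75% | 87.5% |
| Steady prior trend, old follow-up values dropped, baseline left old (T/3) | 100% | 133% | 200% | 400% |

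The last row arises because the two draws are then T months apart, not 3.

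The shrinkage in the first two rows is not a general bound. Suppose half the patients are tested 3-monthly and change by -2.0 log10, and half are tested 6-monthly and change by -0.2. Then 25% of 3-month values are pre-exposure. The observed mean change is (-2.0 - 0.1)/2 = -1.05 against a true (-2.0 - 0.2)/2 = -1.10, so 95% is kept.

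**Selection on viral load.** The simulation assumes a stable true level, no effect, selection on a value of at least log10(40), and a two-sided paired t-test with n = 40. Source mean and SDs are assumptions. Ranges cover undetectable values coded 40, coded 20, or left uncensored.

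| Source mean (log10) | Between / within SD | Mean change | Tests significant |
|---|---|---|---|
| 1.5 | 1.0 / 0.8 (most extreme) | -0.21 / -0.30 / -0.42 | 33 / 52 / 70% |
| 1.5 | 1.0-1.2 / 0.5 | -0.08 to -0.19 | about 13-41% |
| 3.0 | 1.0-1.2 / 0.5-0.8 | -0.03 to -0.13 | 6-11% |
| 3.5-4.0 | 1.0-1.2 / 0.5-0.8 | -0.01 to -0.08 | 5-7% |

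With within-person SD 0.2 to 0.5, between-person SD 1.2, source means 1.5 to 3.0 and undetectable coded 40, the mean fall is 0.004 to 0.08 log10, and 2 to 19% retest below 40. A stable level does not describe patients just starting ART.

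**The case against.** The strongest reply is that harm is possible but not shown. With 3-monthly tests reported by the visit, no 3-month value pre-dates exposure. The stated reason for the visit spacing, and the SAP's description of values as measured at each time point, both fit testing at about that rate. This stands as a limit on the claim: the rule permits the error, and nothing shows that it occurred. It does not remove the point, because neither statement ties a result to a visit.

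The problem is also concentrated at month 3. With tests every 6 months or more often, no 6- or 9-month value pre-dates exposure. That stands too.

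A reader might infer that the bias runs towards zero, or that it flatters the intervention. The documents support neither: the sign turns on prior trend and on who gets tested. The new-patient covariate does not settle it. It is listed with time and without an interaction, so it adjusts level and not trajectory or result age.

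A reader might also infer that any fall in viral load is an artefact and should be reported only descriptively. The large figures come from one corner of an assumed grid, with a source mean below the 40-copy cut-off, and they fade to near nil at higher means. They justify a caveat and a coding rule, no more. That baseline is the qualifying result is itself an inference; no sentence says so.

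Finally, this is a pilot. That lowers the stakes, but Aim 3 is an effect aim and the SAP tests change from baseline.

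**Conclusion.** The concern holds in a limited form. The stated rule can enter a CD4 count or viral load drawn before or on the day of first exposure as a follow-up primary outcome, contrary to Aim 3, and it allows an old baseline. The exposure is mainly at month 3: 0 to 75% of values for assumed test intervals of 3 to 12 months, and all of them if results drawn at visits are reported only later. The true share and the direction of bias cannot be determined without draw dates.

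For viral load only, selection on the baseline value may produce some fall with no effect, from near nil to about 0.4 log10 at the extreme of the assumed inputs. The documents do not support saying that the 3-month results are mostly stale or that the observed changes are spurious. The plan should be amended, with medium confidence in how much it matters.

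**What to change.** 1. Protocol, Study Design and Measures: record the specimen date of every CD4 and viral-load result, including baseline.
2. SAP, GEE analysis: do not count a result drawn on or before the enrolment day as a follow-up outcome, and do not enter one result at two visits; set that visit's value missing. Keep every distinct result drawn after first exposure. Add a supporting GEE that uses actual draw time, including the baseline draw date, in place of nominal visit.
3. Report at each visit the age of the result, the time between draws and the share drawn before exposure, by new or established status. Show the current latest-value analysis alongside, because dropping old follow-up values while the baseline stays old can overstate change under a prior trend (the 133 to 400% above).
4. State how undetectable viral load is coded before the log is taken, and state when interpreting its change that baseline was selected as detectable.

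**Cost.** One date field, a return to the charts (the SAP is in the past tense, and this assumes the charts hold dates) and a little more analysis; no new tests. Some visit values become missing. With 40 retained, about 40, 30, 20 or 10 have a new result at each visit under 3-, 4-, 6- or 12-monthly testing (40 × 3/T). At month 3 the rest are pre-exposure values. At months 6 and 9, with tests every 4 or 6 months, the rest are repeats of a result already counted. Missingness may depend on who is tested, so it may not be at random, and the GEE should be read with that in mind.
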